**Table 2. Sample size and power**

Cohort size N (Total sample)	Loss to follow-up or noncompliance	Unpaired t- test	Fisher exact test			
			Effect size 	Power (%)	Effect size 	Power (%)
117 (234)	40%				0.30 (p1=0.8, p2=0.50)	95.4
100 (200)	30%	0.5	83.6			
167 (334)	40%				0.25 (p1=0.8, p2=0.55)	95.8
143 (286)	30%	0.5	94			
250 (500)	40%				0.20 (p1=0.8, p2=0.6)	96
215 (430)	30%	0.4	93.2			
334 (668)	40%				0.15 (p1=0.8, p2=0.65)	96
286 (572)	30%	0.3	84.9			

1 standardized mean difference of 2 groups  
2 absolute proportion difference of 2 groups with proportions ( $p_1 = P(\text{above MID in pre-training cohort})$ ,  $p_2 = P(\text{above MID in post-training cohort})$ )

**Missing data:** We will make every effort to prevent and avoid missing data. Even with the most robust processes, however, some missing data is inevitable. We will assess the mechanism of missing data by comparing patients with and without missing values on baseline and other complete information, to detect any patterns in demographics or other characteristics associated with missing data. First, the various missingness assumptions (missing completely at random: MCAR, missing at random: MAR or missing not at random: MNAR) will be tested by comparing subjects with missing and non-missing data. In order to incorporate uncertainty in handling missing data, we will perform a multiple imputation, which begins with a prediction of the missing data using the existing data from other variables. The missing values will then be replaced with the predicted values, and a full data set called the imputed data set will be created. This process iterates the repeatability and makes multiple imputed data sets. Each multiple imputed data set produced will be then analyzed using the standard statistical analysis procedures for complete data, and give multiple analysis results. Subsequently, by combining these analysis results, a single overall analysis result will be produced.

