### 11.5 Please provide a justification for your sample size

In order to achieve a statistical power of greater than 80% at an effect size of 0.3, we require a minimum of 200 participants to complete all follow-up in each cohort of the study, as detailed in the power analysis in Section 11.6. In order to account for a roughly 30% rate of attrition, we are requesting a sample size of 300 participants per arm, for a total of 600. Based on previous longitudinal studies by team members [name], [name], and [name], we believe that this is a conservative estimate considering the duration of each participant's involvement.

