## 11.6 Data Analysis Plan: Complete description: Background, Objectives, Design, Step by Step how the project is going to be done, Data analysis plan:

In order to assess for significant differences between two cohorts of patients, bivariate comparisons will first be conducted using a Chi-squared (Fisher exact) test to compare proportions of categorical (dichotomous outcomes) and an unpaired t-test for mean changes of continuous outcomes (i.e. Pain Disability Index scale, self-efficacy, positive outcome expectation, catastrophizing, fear avoidance beliefs and distress).

Alternatively, Wilcoxon nonparametric counterpart will be used for continuous variables where there is deviation from normality. These univariate analyses will be followed by multivariable regression methods for an adjustment of all other potential confounding variables. We will also use longitudinal logistic models (i.e., mixed-effects regression models with a random subject effect and GEE with exchangeable and independent correlations) to analyze the changes of the outcome at baseline at all follow-up times (baseline, post-treatment, at 6 months, and 1 year). Psychological outcomes will be analyzed at baseline and at post-treatment (approximately 4 weeks of enrollment). The models will be specified with random intercepts and slopes such that a linear trajectory representing outcomes will be compared between two arms. For example, longitudinal changes in all available continuous psychological outcomes over time of follow-up will be displayed using locally weighted smoothing scatter (lowess) plots, identifying nonparametric mean trajectories over time. Mean trajectories then will be modeled with mixed-effects linear regression models, and if necessary using segment-linear models to approximate non-linear mean trajectories for ease of interpretation. Group (arm)-specific (as well as individual-level) intercepts and slopes over the period of follow-up will be included as random effects, while other covariates such as other clinical or demographic confounders will be modeled as fixed effects. An interaction term will be also assessed to test group differences in outcomes over time. Residual-based diagnostics will be used to evaluate validity of model assumptions. Two sided p-values <0.05 will be considered to be statistically significant. All statistical procedures will be performed using R statistical package ([www.R-project.org](http://www.R-project.org)).

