In order to determine the association of treatment effects among the subjects who endorse the mental care questions, we will further perform the sub-analysis using the regression analysis similarly stated as above. All covariates and their source are shown in the tables of variables found in Section 10.2. This analytic approach will be hypotheses generating and will be largely exploratory as the study may not be powered to detect significant effects. Therefore, we have not proposed any formal power calculation for the sub-analysis.

Assuming normality, we calculated the statistical power for various detectable effect sizes and sample sizes in a two-sided hypothesis test with a significance level of 0.05, where the ratio of sample size of 1:1 is assumed between cases (intervention arm) vs. controls. When outcomes are proportions, we calculated power based on rate differences. Table 2 shows that our sample size will have adequate power to detect listed effect sizes. For example, we will achieve 95.4% power to detect a difference of rate of 0.3 (i.e., achieving minimal clinically important difference of 80% in receiving therapy by PT staff "after training" group vs. 50% in receiving therapy by PT staff before training) between two arms of a size of 100 (117) for each with 30 (40) % of missingness. For continuous outcomes, the same size of n=100 (117) for each will have a 83.6% power to detect standardized mean difference of 0.5, which corresponds that the reduction in PDI (Pain Disability Index) score from baseline to follow-up would be 50% greater in the training group as compared to that before training. Note that for each domain outcome, the power is the same for each effect size since they are standardized, but the mean change corresponding to a given effect size differs.

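### Table 2's bolded binary row states 96% power for 0.80 versus 0.65; the two-sided Fisher exact test at that row's own inputs gives 90.7%

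*Combined protocol and SAP*

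**What the plan says.** Section 11.6 says that power was calculated for a "two-sided hypothesis test with a significance level of 0.05", and that "the ratio of sample size of 1:1 is assumed between cases (intervention arm) vs. controls". The analysis paragraphs of the same section use the same threshold: "Two sided p-values <0.05 will be considered to be statistically significant".

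Table 2 heads its proportion columns with the Fisher exact test and applies 40% loss to each cohort size in them. The bolded binary row has 334 per cohort (668 in total), an effect of "0.15 (p1=0.8, p2=0.65" (closing bracket omitted here) and a stated power of 96%. The companion bolded t-test row has 286 per cohort, 30% loss, a standardized difference of 0.3 and a power of 84.9%.

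Section 11.5 justifies the sample size by requiring "a minimum of 200 participants to complete all follow-up in each cohort", for power above 80% at an effect size of 0.3.

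Footnote 2 to Table 2 defines p1, which is 0.8 in every row, as the probability of being "above MID in pre-training cohort". The worked example in Section 11.6 gives the 80% to the after-training "group vs. 50% in receiving therapy by PT staff before training".

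**The concern.** The pattern of the binary rows raises the question. As completers per arm rise from 70 to 100 to 150 and the difference falls from 0.30 to 0.25 to 0.20, stated power stays near 95 to 96%. The last step, to 200 completers and a difference of 0.15, keeps the same 96%. Between the third and fourth rows the sample grows by a third (200/150 = 1.33). Holding power with a difference cut from 0.20 to 0.15 needs roughly (0.20/0.15)² = 1.78 times as many, before allowing for the small change in variance. So 96% looked too high.

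This is one of the two rows the plan puts in bold, and both correspond to the 200-completer target of Section 11.5. A reader planning a responder analysis from it would believe that 200 completers per arm detect a 15-point difference with a 4% risk of missing it.

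**Working it through.** **Inputs, all from the plan**
- Test: Fisher exact (Table 2 column header).
- Two-sided, alpha 0.05, 1:1 allocation (Section 11.6).
- Rates in the bolded row: 0.80 and 0.65.
- Completers per arm: 334 x (1 - 0.40) = 200.4, taken as 200. This agrees with the 200-per-cohort minimum in Section 11.5.

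**Method**

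Power = sum over all pairs (x, y) of Bin(x; n, p1) x Bin(y; n, p2), counting only pairs whose two-sided Fisher p-value is at most 0.05. Every pair is enumerated, with no simulation or approximation. The two-sided p-value is the sum of the hypergeometric probabilities no larger than that of the observed table. Doubling the smaller tail gives the same power to four decimals in all four rows.

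**Binary rows**

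| Cohort size | Completers per arm | Rates | Printed | Two-sided Fisher |
|---|---|---|---|---|
| 117 | 70 | 0.80 / 0.50 | 95.4 | 95.42 |
| 167 | 100 | 0.80 / 0.55 | 95.8 | 95.85 |
| 250 | 150 | 0.80 / 0.60 | 96 | 96.02 |
| **334** | **200** | **0.80 / 0.65** | **96** | **90.68** |

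**t-test rows** (noncentral t, df = 2n - 2, noncentrality d x sqrt(n/2), n = cohort size x 0.7)

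| Cohort size | Completers per arm | d | Printed | Recomputed |
|---|---|---|---|---|
| 100 | 70 | 0.5 | 83.6 | 83.58 |
| 143 | 100 | 0.5 | 94 | 94.04 |
| 215 | 150 | 0.4 | 93.2 | 93.23 |
| 286 | 200 | 0.3 | 84.9 | 84.91 |

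Seven of the eight cells reproduce to within rounding, so the table identifies its own method. Only the bolded binary cell fails: 96 - 90.7 = 5.3 points.

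**Could another calculation give 96 in that row?**
- Rounding up to 201 completers: 90.79%.
- Ignoring the loss (334 per arm): 99.03%.
- Using 30% loss (234 per arm): 94.6%.
- Swapping which arm has 0.80: 90.68%, unchanged.
- Other two-sided methods at 200 per arm: uncorrected chi-square 92.36%, continuity-corrected chi-square 90.61%, continuity-corrected normal approximation 90.4%, pooled normal 92.21%, unpooled normal 92.62%, arcsine 92.34%.
- One-sided methods at 200 per arm: Fisher 94.97%, uncorrected chi-square 96.00%. The latter matches the cell but contradicts the stated two-sided test. It would also give 98.51%, 98.69% and 98.57% in the other three binary rows, where 95.4, 95.8 and 96 are printed.

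**Size in practical terms** (two-sided Fisher)
- Miss probability at 200 per arm: 100 - 90.7 = 9.3%, against an implied 100 - 96 = 4%.
- Difference detectable with about 96% power at 200 per arm: 0.80 versus 0.63 gives 95.93%, so about 0.17 rather than 0.15.
- Completers needed for about 96% power at 0.80 versus 0.65: 250 per arm gives 95.82%, 256 gives 96.25%.

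**The case against.** The strongest reply is that nothing depends on this cell. Section 11.5 sizes the study on the t-test row, which is correct, and the worked example in Section 11.6 uses the first binary row, also correct. The general statement of adequate power survives at 90.7%. No binary primary outcome is named, so a 0.15 difference is a grid scenario rather than a committed hypothesis. All of this stands, and it keeps the point minor.

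The row is also not the enrolled design. Sections 11.2 to 11.5 plan 300 per arm with roughly 30% attrition: 300 x 0.7 = 210 completers, for which two-sided Fisher power is 92.1%. With 40% loss, 300 x 0.6 = 180 completers give 87.2%. The 9.3% miss probability therefore describes the row and the 200-completer minimum, not the rate expected under planned enrolment. That is a fair limit on the size, but the cell is still wrong for the inputs printed beside it.

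The replacement value could be said to depend on method, since Section 11.6 names chi-squared alongside Fisher and invokes normality. The two-sided alternatives run from 90.4% to 92.6%, all well short of 96%. The column header and the three matching rows settle on Fisher.

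Finally, the slip could lie in another entry of the row: p2 = 0.63 would give 95.9%. But 0.15 continues the sequence 0.30, 0.25, 0.20, and 334 x 0.6 = 200 continues 70, 100, 150. The power entry is the one that does not fit. How the error arose cannot be told from the documents.

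**Conclusion.** The stated power is wrong. At 200 completers per arm, rates 0.80 and 0.65 and a two-sided Fisher exact test at 0.05, power is 90.7%, not 96%: an overstatement of 5.3 points, with the miss probability 9.3% instead of 4%. This rests only on the row's printed cohort size, loss and rates, and on the test and significance level the plan states. It is a minor, isolated erratum: the sample size, the tests and the claim of power above 80% are unaffected.

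The conflict between footnote 2 and the worked example is a separate labelling slip. It neither causes the wrong cell nor changes any power value.

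**What to change.** In Table 2, row 334 (668), replace 96 with 90.7, after the study statistician has confirmed that the printed cohort size, loss and rates are the intended ones.

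In the same edit, correct footnote 2 so that p1 is the post-training cohort and p2 the pre-training cohort. The worked example states that direction only for the 0.30 row; extending it to all rows is an inference, but the natural one, since p1 is 0.8 throughout and the study hypothesises benefit after training.

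The cost is one table cell and one footnote label. Enrolment, tests and analysis do not change.

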## 12.0 Participant Information

### 12.1 Subject Population:

US active duty service members receiving physical therapy for musculoskeletal disorders at Naval Medical Center Portsmouth and its branch health clinics.

### 12.2 Age Range:

Check all the boxes that apply. If the age range of potential subjects (specimens, records) does not match the range(s) selected, please specify in the text box.

- 0-17
- 18-24
- 25-34
- 35-44
- 45-54
- 55-64
- 65-74
- 75+

### 12.3 Gender:

- Male
- Female
- Other

### 12.4 Special categories, check all that apply

- Minors /Children
- Students
- Employees - Civilian
- Employees - Contractor
- Resident/trainee
- Cadets /Midshipmen

- Active Duty Military Personnel
- Wounded Warriors
- Economically Disadvantaged Persons
- Educationally Disadvantaged Persons
- Physically Challenged (Physical challenges include visual and/or auditory impairment)
- Persons with Impaired Decisional Capacity
- Prisoners
- Pregnant Women, Fetuses, and Neonates
- Non-English Speakers
- International Research involving Foreign Nationals - Headquarters Review is necessary

You must also consider the requirements of DoDI 3216.02, Enclosure 3, paragraph 7.e.

#### 12.5 Inclusion Criteria:

Order Number	Criteria
1	Active duty service members (at baseline; separation from the military post-treatment will not be grounds for exclusion)
2	Patients presenting to an NMCP or branch clinic physical therapy department
3	Patients who have only received their evaluation appointment for their primary complaint
4	Patients presenting for a primary complaint of a MSD (The following ICD-10 codes will be included: M13,M14.8,M15-19,M21-25,M40-43,M46-48,M50- 54,M60-71, M73,M75-77)

#### 12.6 Exclusion Criteria:

Order Number	Criteria
1	Patients not eligible to receive outpatient physical therapy.
2	Patients receiving fewer than four treatment sessions of physical therapy.
3	Patients who are pregnant
4	Patients receiving physical therapy for acute post-surgical recovery
5	Patients scheduled for or subject to a Physical Evaluation Board (PEB) at baseline
6	Coast Guard, as they are DoT rather than DoD

### 13.0

#### Recruitment and Consent

##### 13.1 Please describe the recruitment process, including how subjects will be identified and selected for the study.

Research staff will approach pre-screened patients immediately after their evaluation appointment with their physical therapist, inform them of the study, and ask them if they are interested in participating. Interested patients will then be lead to a private study area nearby to begin the consenting process described in Section 13.4. Those who consent will leave us their contact information and may complete their baseline questionnaire immediately on location, or they may complete it remotely before their next appointment.

### **13.2 Compensation for Participation:**

Participants will not be compensated for participation.

### **13.3 Please describe the pre-screening process. If no pre-screening, enter Not Applicable in the text editor**

Physical therapy staff will be informed of the inclusion and exclusion criteria for our study. Researchers will use printouts of the clinic schedule received from the clinic manager to determine which patients are coming in for evaluation. In Phase II, we will also use the schedule to verify that the patient's therapist has completed PiPT training. We will let staff members conducting evaluations know that we are interested in approaching their patients after the evaluation if they are eligible. If the staff member assents, we will brief the patient on the study and ask them to verify that they are:

1. An active duty service member beginning physical therapy for their current musculoskeletal injury
2. NOT pregnant, receiving PT for post-surgical follow-up, or scheduled for or subject to a Physical Evaluation Board.

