We found evidence for the effectiveness of PiPT in the carrier study as well. Subjects in the intervention arm reported learning coping strategies that are associated with good outcomes. Responses to the question "Please list the most important things you learned in physical therapy?" differed between the two groups. Among subjects on the intervention carrier, 33.7% indicated they had learned concepts consistent with PiPT treatment based on a priori analysis criteria developed by the investigators. For example, one intervention subject said, "Stress and physical pain have a connection". In contrast, none of the subjects from the control carrier responded in this manner. Our experience with PiPT training has informed the development of the present proposal.

In our interdisciplinary training for the RCT described above, we avoided some of the weaknesses highlighted in previous studies by giving specific examples of how to implement guideline-based care for each discipline and by providing weekly teleconferences to answer questions, discuss difficult cases and reinforce training. In addition, we encouraged the use of self-care techniques to reduce patient reliance on health care professionals. This further distinguished our approach from Overmeer's. In our training for US Navy PT staff aboard a carrier we replicated our original training while incorporating important aspects found to be effective in other studies, such as ongoing role-playing and case-examples once the PT staff was deployed through teleconference.

The long-term objective of our research is to implement PiPT in different settings and for different cohorts of patients with MSD, throughout the Military. Therefore, we propose a full-scale study replicating the design and methods used in our pilot carrier study to test the feasibility and short- and long-term effectiveness of PiPT on psychological and functional outcomes in ADSM seeking care for MSD at a shore based rehabilitation setting; Navy Medical

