##### Phase I

###### Recruitment and Consenting

- Research staff will review the PT clinic's schedule for patients scheduled for initial evaluation, then request an introduction from the therapist if appropriate (patient must be scheduled for at least 4 physical therapy sessions).
- Research staff will brief the patient on the study.
- If the patient is interested, the researcher will show them to the private study room, screen them for eligibility, and then ask them to review the consent form. The researcher will remain in the room to answer any questions.

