###### Treatment

- After signing the consent form, the participant will complete a paper form collecting contact information for follow-up and demographic information. At this point, the participant will be assigned a participant ID number. The researcher will verify the participant's diagnostic code and therapist using AHLTA afterward.
- Before the participant's next PT appointment, the participant will complete the baseline questionnaire battery, a 139 question survey battery. The participant may complete the battery immediately on paper, or at a later date online using a link to REDCap that will be sent via encrypted email. This battery must be completed before their next appointment.
- Participants will receive standard PT care as prescribed and scheduled by their therapist. Participation in the study will not alter their care plan.
- Participants will complete follow up questionnaire batteries after their 4th PT appointment\*, 6mo and 12mo post enrollment. The first follow-up questionnaire is a 77 question survey battery. The second and third follow-up points use a 68 question battery. All follow-up questionnaires will be completed remotely via REDCap.
- We will collect de-identified SOAP notes from randomly selected participants and review them for verbiage indicating that the therapist employed principles of PiPT. We will collect up to 30 SOAP notes, pertaining to various physical therapists and throughout various stages of treatment.

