##### PT Training

Following the completion of Phase I recruitment, PT staff will be trained in PiPT by the NYU personnel. NYU personnel intend to deliver the training in person; however, they are prepared to deliver virtual, real-time training should COVID protocols make face-to-face training unfeasible.

- PT staff will receive a knowledge quiz at the end of their training sessions to document successful completion of training. PT staff must obtain a passing score (85% or above) on this quiz to be considered proficient.
- We will also assess the PT staff's confidence in implementing PiPT using a seven point Likert scale self-rating derived from a previous study.
- Furthermore, staff will be evaluated on the accurate identification and management of yellow flags using case studies.
- Once the staff shows proficiency in delivering PiPT, the second study phase will begin. There will likely be some overlap between the follow-up data collection of Phase I and the training period.
- After initial training and as Phase II recruitment begins, staff will receive weekly reinforcement sessions for one month, after which they will receive further reinforcement sessions on a biweekly basis as needed.

During training, PT staff will be asked whether they have had previous experience with PiPT. If so, participants who saw these providers, whether during Phase 1 or 2, will be analyzed for a possible confounding effect.

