### Treatment

- After signing the consent form, the participant will complete a paper form collecting contact information for follow-up and demographic information. At this point, the participant will be assigned a participant ID number. The researcher will verify the participant's diagnostic code and therapist using AHLTA afterward.
- Before the participant's next PT appointment, the participant will complete the baseline questionnaire battery, a 139 question survey battery. The participant may complete the battery immediately on paper, or at a later date online using a link to REDCap that will be sent via encrypted email. This battery must be completed before their next appointment.
- Participants will receive PT care as prescribed and scheduled by their therapist. Participation in the study will not directly alter their care plan.
  - During Phase II, we anticipate that therapists who completed PiPT training will incorporate the training into their standard care. We will not ask therapists to give differential treatment to patients who are enrolled in the study.
- Participants will complete follow up questionnaire battery after their 4th PT appointment, 6mo and 12mo post enrollment. The first follow-up questionnaire is a 77 question survey battery. The second and third follow-up points use a 68 question battery. All follow-up questionnaires will be completed remotely via REDCap.
- We will collect de-identified SOAP notes from randomly selected participants and review them for verbiage indicating that the therapist employed principles of PiPT. We will collect up to 30 SOAP notes, pertaining to various physical therapists and throughout various stages of treatment.

We chose to conduct this study in sequential cohorts rather than conducting the two cohorts (PiPT and non-PiPT) in parallel because there are no comparable sites with similar characteristics such as type of subjects, catchment area size and availability of the health care team in the Navy.

\*We chose the 4th visit as the first follow-up point for two reasons. First, we expect to see a difference between groups on study outcomes at that point. Secondly, since according to the former head of the NMCP department of physical therapy (PI) the average number of visits at the outpatient PT clinic is 6, the 4th visit will allow us to capture complete data.

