#### **14.5 Privacy for Subjects:**

Describe the measures to protect subject's privacy during recruitment, the consent process, and all research activities, etc.

Recruiting and consenting: We intend to rely on physical therapy staff to introduce us to eligible patients in their exam room after their evaluation session, so that participants can be briefed on the study in private. Interested patients will be provided a private space in the PT clinic to review the consent form and ask questions.

Participation: Participants may either complete their baseline questionnaire in person or online; all follow-up questionnaires will be completed remotely. If they choose to participate in person, they will complete the questionnaire in paper in the consenting area. The online method will consist of the research team sending a link to the online questionnaire via encrypted email to the address specified by the participant. The online questionnaire will be hosted on REDCap.

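### The treating therapist, whose training defines the two cohorts, controls introduction to the study and the number of sessions booked, so selection could shift at the training date without being seen

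*Combined protocol and SAP*

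**What the plan says.** Entry passes two points that the treating therapist controls.

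**Introduction.** Under 10.1 (Phase I, Recruitment and Consenting), research staff find evaluation patients on the clinic schedule, "then request an introduction from the therapist if appropriate (patient must be scheduled for at least 4 physical therapy sessions"). Section 13.3 adds: "If the staff member assents, we will brief the patient on the study". Section 14.5 says: "We intend to rely on physical therapy staff to introduce us to eligible patients in their exam room after their evaluation session". Section 13.1 places the approach straight after the evaluation appointment, so the therapist has already assessed the patient.

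**Session booking.** Four booked sessions are needed at entry. Bookings are the therapist's in both phases: "Participants will receive standard PT care as prescribed and scheduled by their therapist" (Phase I) and "Participants will receive PT care as prescribed and scheduled by their therapist" (Phase II). Section 12.6 words the criterion differently and excludes "Patients receiving fewer than four treatment sessions of physical therapy".

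**What changes between phases.** Section 10.1 (PT Training) says: "Following the completion of Phase I recruitment, PT staff will be trained in PiPT by the NYU personnel". Phase II recruitment is otherwise to run largely as in Phase I, with an added check that the therapist has completed training.

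**Safeguards.** Section 13.3 has staff told the eligibility criteria. Aim 2 (9.3) compares baseline risk factors. Section 11.6 plans t-tests on mean changes, then multivariable regression and mixed models. The protocol describes no log of patients evaluated, introduced, declined or booked for fewer than four sessions.

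**The concern.** In a before-and-after comparison without randomisation, anything that moves at the training date is confounded with the intervention. Here the person who is trained also decides who is introduced and how many sessions are booked. Training covers recognition of yellow flags, which section 9.2 treats as prognostic, so a trained therapist may judge suitability or plan a course of visits differently. The four-session threshold is not far below the average of six visits given in 10.1, so a modest change in booking could alter who qualifies.

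At stake is the Aim 3 conclusion. A shift towards easier patients in Phase II would look like a PiPT benefit; a shift towards harder ones would hide a real benefit. Without counts by phase, neither can be shown or ruled out.

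**Working it through.** **Inputs from the plan.** Two-sided 5% test (11.6); standardised difference 0.3, 200 completers per cohort and about 30% attrition (11.5); 300 enrolled per arm (11.4). Expected completers: 300 × 0.70 = 210 per arm.

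**The plan's own figure.** In the last t-test row of Table 2, 286 × 0.70 ≈ 200 per arm. The noncentrality is 0.3 × √(200/2) = 3.0, and the noncentral t gives 84.9% power, as stated. The t-test power figure is not in question.

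**Assumed selection.** The documents give no size for this, so everything below is assumption. Score the therapist's judgement as a standard normal, higher meaning better prognosis, and withhold the lowest fraction q in Phase II only. The mean judgement of those entered rises by m = φ(z_q)/(1 − q).
- q = 0.10: m = 0.1755/0.90 = 0.195.
- q = 0.20: m = 0.2800/0.80 = 0.350.

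**Unadjusted comparison at follow-up, no PiPT effect, 210 per arm.** The shift is m × r, where r is the correlation of judgement with outcome.
- q = 0.10, r = 0.5: 0.195 × 0.5 = 0.0975 SD, about a third of 0.3. Noncentrality 0.0975 × √105 = 1.00; rejection 16.9%.
- q = 0.10, r = 0.3: rejection 9.2%. With r = 0.2: 6.8%.
- q = 0.20, r = 0.5: shift 0.175 SD; rejection 43.2%.

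**Analyses of the kind 11.6 plans, q = 0.10, r = 0.5.** Let a be the correlation of judgement with the baseline score and b that of baseline with follow-up, with equal SDs.
- Standardised change-score shift: m(0.5 − a)/√(2 − 2b).
- Standardised baseline-adjusted shift: m(0.5 − ab)/√(1 − b²).

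| a | b | Change-score shift | Rejects | Adjusted shift | Rejects |
|---|---|---|---|---|---|
| 0.5 | 0.5 | 0 | 5.0% | 0.056 | 8.9% |
| 0.6 | 0.6 | −0.022 | 5.6% | 0.034 | 6.4% |
| 0.3 | 0.5 | 0.039 | 6.8% | 0.079 | 12.7% |

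The range is 5% to 13%. The change-score shift can even reverse sign. With q = 0.20, the same formulas with m = 0.350 give 5% to 11% for change scores and 10% to 30% for the adjusted analysis.

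**A second way to set the assumption.** If one phase omits 10% of eligible patients whose mean outcome lies D SDs from the overall mean, the shift is 0.1D/0.9. For D = 0.5 to 1.0 this is 0.056 to 0.111 SD, or 19% to 37% of 0.3. The unadjusted rejection rate at 200 per arm is 8.6% to 19.8%.

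**Opposite direction.** With a true effect of 0.3 and a 0.10 SD shift against it, unadjusted power at 200 per arm falls from 84.9% to 51.4%.

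**The case against.** Four points on the other side carry weight.

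1. *The entry steps are written alike.* Assent and introduction apply in both phases. A reader might infer that the cohorts will be selected differently, or in PiPT's favour. The documents do not show this: they establish neither a difference in prognosis nor its direction. Therapists trained to manage yellow flags might introduce more such patients. The one written difference is the trained-therapist check in Phase II.

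2. *Discretion is not wholly open.* Staff are told the criteria, 13.3 and 14.5 refer to eligible patients, and 14.5 gives privacy as the reason for the introduction. That stands. But assent in 13.3 comes on top of eligibility, and no rule bars refusal on other grounds.

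3. *Nothing shows that training changes bookings.* Section 9.2 says of an earlier interdisciplinary training that "we encouraged the use of self-care techniques to reduce patient reliance on health care professionals". One might read this as evidence that PiPT therapists will book fewer visits. It states an intention, reports no effect, and says nothing about a four-session threshold.

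4. *The planned analysis absorbs part of any shift.* The baseline battery covers pain interference, catastrophizing, fear avoidance, self-efficacy and distress, which are plausible grounds for selection. The 17% and 43% rates are therefore not error rates of the planned analysis. But adjustment reaches only what is measured in people who enrolled. The battery is also completed after the evaluation visit, so in Phase II it may already reflect contact with a trained therapist.

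**Conclusion.** The concern holds as a statement about control and visibility. The person whose training defines the cohort controls introduction and booking, so selection could shift at the training date, and nothing planned would reveal it. Aim 2 and the regression reduce the problem without closing it.

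The size is unknown. In the illustrative case (10% withheld in Phase II only, judgement correlating 0.5 with outcome, no true effect, 210 per arm), a nominal 5% test rejects about 17% of the time unadjusted and about 5% to 13% under the planned kinds of analysis, depending on the assumed baseline correlations. These figures show that modest selection would matter against a design effect of 0.3. They do not predict that it will occur. The change is worth making because it is cheap and because non-introductions cannot be reliably reconstructed afterwards.

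**What to change.** In 10.1 and 13.3, from Phase I onward:

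- Seek to approach every consecutive evaluation patient on the schedule printout.
- Limit therapist non-introduction to a listed reason under 12.5 or 12.6, or the patient's own refusal.
- Keep an aggregate, non-identifying tally by phase and therapist: evaluated; not introduced, with reason (including fewer than four sessions booked, as reported by the therapist); introduced; consented. Do not open records of patients who have not consented. The printout is not said to show pregnancy, evaluation-board status, surgical status or diagnosis, so reasons must come from the therapist or the patient.
- Report the tally by phase, and state any shift in the introduction or booking share as a limit on the Aim 3 conclusion.

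Separately, reconcile the four-session criterion: 10.1 refers to sessions scheduled, which is known at entry, whereas 12.6 refers to sessions received, which is known only later and sits badly with the intent-to-treat statement in 11.1.

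Cost: a little more staff time and slightly less therapist discretion. Patient care, outcomes and sample size are unaffected.
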